## Rationale

Despite major advances in the treatment of mood disorders, depression remains a serious public health problem. In a recently published Sequenced Treatment Alternatives to Relieve Depression (STAR\*D) trial, patients had remission rates of 37%, 31%, 14% and 13% for four distinct types of pharmacotherapy treatment. Another limitation to pharmacological treatment is the delayed response, which can often take up to several weeks and is especially deleterious for suicidal patients. For these reasons, electroconvulsive therapy (ECT) represents an important and efficacious treatment modality for the treatment of depression. ECT generally provides faster amelioration of depressive symptoms and its efficacy is reported to be 65 to 85%. However, even with ECT some patients do not respond and the antidepressant response requires multiple sessions increasing risk of impaired cognitive function, which still remains the limiting factor in its use.

Ketamine is a non-barbiturate anesthetic that has been used infrequently as an anesthetic in ECT. As ketamine has no anticonvulsant properties as barbiturate anesthetics do, its use has been generally reserved for instances when a seizure cannot be elicited from a patient despite the application of maximum device settings. However, there are recent reports that demonstrate ketamine's favorable seizure and cognitive profile.

Furthermore, ketamine is hypothesized to possess intrinsic antidepressant properties when used as monotherapy for depression. Several investigators have determined that ketamine, at sub-anesthetic doses, alleviates depressive symptoms in animals. There is some recent evidence that the use of ketamine in ECT may enhance the overall outcome. A non-randomized trial by Okamoto shows a faster response when ECT is given with ketamine anesthesia compared to that with propofol. We propose a pilot study to measure both therapeutic efficacy and cognitive side effects of ECT using ketamine compared to methohexital in depressed patients.

Although electroconvulsive therapy (ECT), regardless of the anesthetic agent, is a highly effective form of treatment in major depression, very little is known about the underlying mechanism of action. Neuroimaging is a non-invasive technique which may provide more insight into the underlying changes in the neurophysiologic circuitry. Several PET investigations

have examined regional changes in blood flow or glucose consumption before and after ECT. However, the results of these studies were sometimes contradictory and this type of methodology was not suited to detect possible changes in brain networks. In this last decade novel fMRI techniques have became available to measure and evaluate networks in the brain. Hence, in this pilot study, we will also collect longitudinal MRI data (once before ECT and twice after ECT) to gain novel insight into the effect of ECT at a deeper level.

In addition, we will also explore other parameters of ECT, such as seizure duration and morphology as well as hemodynamic and behavioral changes when using ketamine versus methohexitol for ECT.

## **Specific Aims**

### **Primary Aims**

To compare the efficacy of ECT with ketamine anesthesia to that with methohexitol for depressed patients undergoing an acute course of standard ECT treatment as defined by the time needed to achieve remission. We will also characterize the temporal pattern of improvement in depression between the two treatment groups.

### **Primary outcome**

The primary outcome will be the time to achieve remission. Remission is defined as two consecutive HRSD24 scores < 10, and HRSD24 total score does not increase > 3 points on the second consecutive HRSD24, or remains < 6 at the last two consecutive treatments. HRSD-24 scores are used to define remission.

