### 1. Study Overview

This is a prospective, random assignment, double blind, parallel group pilot study comparing the efficacy of bifrontal ECT performed with ketamine anesthesia to that performed with methohexitol anesthesia in patients with a major depressive episode. We intend over a 2 year period, to recruit 24 patients who are scheduled to receive an acute course of ECT. Patients who are able and willing to provide written informed consent will be randomly assigned on a 1:1 ratio to receive either a course of bifrontal ECT using ketamine or methohexitol anesthesia. Subjects will receive a standard acute course of ECT (3X/week) and depressive symptomatology will be monitored with the Hamilton Rating Scale for Depression (HRSD-24) before each treatment.

The primary outcome will be the number of treatments needed to achieve remission. Remission is defined as two consecutive HRSD scores  $\leq 10$ , and HRSD total score does not change  $> 3$

points or remains < 6 at the last two consecutive treatments. For the secondary aim of this pilot study we will monitor cognitive changes before and after each ECT treatment, and at the end of the treatment course. In addition, we will collect data on other treatment parameters such as seizure duration, electroencephalogram (EEG) morphology, hemodynamic changes, and emergence of any psychotic symptoms post treatment.

Parallel with these procedures we will also collect magnetic resonance imaging (MRI) data on these subjects. The timeline of neuroimaging and its relation to ECT is illustrated in Figure 1.

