### d. Outcome Criteria

## **1. Remitter criteria**

- (a)  $\geq 60\%$  decrease from baseline in HRSD total score, *and*
- (b) HRSD  $\leq 10$  on two consecutive ratings, *and*
- (c) HRSD does not change  $> 3$  points on last 2 consecutive treatments. We do not define a specific minimum or maximum number of ECT for a patient to be classified as a remitter.

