## **2. Non-remitter criteria**

- (a) patient does not reach above remission criteria, *and*
- (b) has at least 10 treatments, *and*
- (c) reaches a plateau defined as no clinical improvement ( $< 3$  point decrease in HRSD after last 2 consecutive treatments).

*Drop-outs* are patients who discontinue treatment before they can be declared remitters or *non-remitters*. Premature exits in this study will be analyzed as non remitters. Criteria for *premature exits* are as follows:

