### **13. Data Analysis**

To test whether the time to remission is different between the ketamine and the methohexitol groups, a survival analysis will be performed. The outcome event will be remission, and Kaplan-Meier curves will show the percent of patients not in remission as a function of time on study. A log-rank test will be used to test for differences between the time to remission in the two groups. Patients who drop out of the study prior to achieving remission or who continue to the end of the study period without achieving remission will be analyzed as censored at the time of last observation.

For Aim 1, to test whether the rate of change in the HRSD score over time is different in the two treatment groups, a mixed model for longitudinal data will be used. The fixed effects are

treatment group and time on study, and the random effect is subject. The data will be examined to see whether a linear function of time is appropriate. If not, either the data will be transformed to achieve linearity, or another form (e.g., quadratic) of model will be considered. This model will yield estimates for slopes (rates of change in HRSD scores per visit) for each treatment group, and the groups will be compared by testing whether the slopes are significantly different from one another.

For Aim 2, to test whether the rate of change in the various measures of cognitive function over time is different in the two treatment groups, a mixed model for longitudinal data will be used for each of the measures. As above, the fixed effects are treatment group and time on study, and the random effect is subject. The data will be examined to see whether a linear function of time is appropriate. If not, either the data will be transformed to achieve linearity, or another form (e.g., quadratic) of model will be considered. As above, the model will provide estimates of the slopes measuring the rates of change in scores per visit for the two treatment groups; and the treatments will be compared by testing for a difference between the slopes corresponding to the two groups.

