Since this is a pilot study, the goal is to estimate the magnitude of the effect sizes for use in designing a subsequent study. With 12 patients randomized to each of the two treatment groups, there is only 45% power with an alpha level of 5% to detect a difference of 50% remission rate in the methohexital group and an 80% remission rate in the ketamine group at visit 8. For the other aims, which look at the change in scores on various rating scales over time, there will be 80% power with an alpha level of 5% (2-sided) to detect a difference between the slopes (measuring rate of change in scores on tests per visit) for the two treatment groups of magnitude  $0.05\sigma$ , where  $\sigma$  is the standard deviation of scores in either treatment group at a single visit. If, for example, the standard deviation of the HRSD scores is 5.0, then there will be power to detect an increased rate of improvement in the ketamine group of 0.25 points per visit, corresponding to an average improvement of 2.0 more points per 8 visits in the ketamine group than whatever improvement is observed in the methohexital group (Diggle et al 1995).

Given the recognition that, with the small sample size, power will be low, the primary focus of analysis is to determine whether ECT with ketamine anesthesia compared to ECT with methohexital anesthesia produces a clinically significant effect, i.e., one that, even if it does not reach statistical significance, would justify a larger clinical trial to replicate effect size. We expect a mean number of 8 treatments to remission based on the results of a Consortium for Research in ECT paper.

Our specific hypothesis is that ECT will decrease functional connectivity in the Default Mode Network (time-wise hypothesis). We also think that the decrease in the expression of this network will correlate with the effectiveness of the ECT, or at least will show a difference

between responders and non-responders (group-wise hypothesis). In order to detect network changes, we will calculate seed based correlation, ICA network expressions and amplitude measures of the networks.

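### Remission, the event in the primary log-rank test, is defined by three conflicting two-rating rules, and the Data Analysis section does not say which applies

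*Combined protocol and SAP*

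**What the plan says.** Three sections of the combined protocol and SAP define remission by two consecutive HRSD-24 ratings.

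- **Specific Aims, Primary outcome:** both scores below 10, with the condition that the "total score does not increase > 3 points on the second consecutive" rating, or scores staying below 6.
- **Research Design and Methods, 1. Study Overview:** this section also states the primary outcome: "The primary outcome will be the number of treatments needed to achieve remission. Remission is defined as two consecutive HRSD scores" of 10 or less. The stability condition is no change of more than 3 points, with the same alternative route: "points or remains < 6 at the last two consecutive treatments".
- **Section 7d, Outcome Criteria, 1. Remitter criteria:** three conditions, all required. They are a 60% or greater "decrease from baseline in HRSD total score", two consecutive ratings of 10 or less, and no change of more than 3 points. There is no route through scores below 6.

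The Non-remitter criteria depend on the third version. A non-remitter is someone for whom the "patient does not reach above remission criteria", who "has at least 10 treatments", and who has reached a plateau.

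Section 13, Data Analysis, says only: "The outcome event will be remission, and Kaplan-Meier curves will show the percent of patients not in remission". It gives no definition and no cross-reference. It also says that "the goal is to estimate the magnitude of the effect sizes for use in designing a subsequent study".

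Section 6, ECT Procedures, ends the course at remission and describes that as a single score of 10 or less. Table 2 in section 7c schedules one HRSD-24 at 24 to 72 hours after the last ECT.

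**The concern.** A programmer cannot build the primary time-to-event variable from this text without choosing among rules that give the same patient different event times or a different status. If the choice is left open, it could be made after outcomes are known.

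This matters for a pilot. The plan concedes low power and puts the weight on an estimated effect size for a later trial. That estimate, and the visit-8 remission rates of 50% and 80% used for planning, describe an event that is not uniquely defined.

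**Working it through.** **1. Set aside what may be typographical.** The strict cut-off of 10 under Primary outcome could be a lost underline, because the other sections use 10 or less. I use 10 or less throughout and do not count this as a difference.

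**2. The rules side by side.** Let x and y be the first and second of two consecutive ratings, and B the baseline.

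| Rule | Both ≤ 10 | Stability | Both < 6 as alternative to stability | Fall from baseline |
|---|---|---|---|---|
| Primary outcome | yes | y − x ≤ 3 | yes | none |
| Study Overview | yes | \|y − x\| ≤ 3 | yes | none |
| Remitter criteria | yes | \|y − x\| ≤ 3 | no | y ≤ 0.4 × B |

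Section 3 admits baselines from 21. At B = 21, 22, 23 and 24 the last condition requires y ≤ 8.4, 8.8, 9.2 and 9.6. From B = 25 it no longer binds, since 0.4 × 25 = 10.

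**3. Worked patients** (baseline first and not counted as a rating):

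| Scores | Primary outcome | Study Overview | Remitter criteria |
|---|---|---|---|
| 30, 18, 9, 4, 3 | rating 3 | rating 4 | rating 4 |
| 30, 20, 5, 1, 0 | rating 3 | rating 3 | rating 4 |
| 22, 15, 9, 9, then 9 throughout | rating 3 | rating 3 | never |

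In the first row, 9 to 4 is a fall of 5, which only the Primary outcome rule tolerates. In the second, 5 to 1 is a fall of 4, rescued under the Study Overview because both scores are below 6. In the third, 9 exceeds 8.8; after ten treatments this patient is a non-remitter under section 7d. Reading Primary outcome strictly as below 10 changes none of these results.

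**4. Count of score patterns.** There are 11 × 11 = 121 integer pairs with both scores from 0 to 10.

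- Primary outcome: 28 pairs rise by 4 or more, and 3 of these have both scores below 6, so 121 − 28 + 3 = 96 are accepted (82 with a strict cut-off).
- Study Overview: 121 − 56 + 6 = 71.
- Remitter criteria: 121 − 56 = 65 at baseline 25 or more, 65 − 4 = 61 at 23–24, and 65 − 9 = 56 at 21–22.

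The rules nest: every pair accepted by the Remitter criteria is accepted by the Study Overview, and every one of those by Primary outcome. Pairs that are remission under Primary outcome but not under the Remitter criteria number 96 − 65 = 31, 96 − 61 = 35 and 96 − 56 = 40 in the same baseline order. These are equally weighted patterns, not patient frequencies.

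**5. Size per affected patient.** One rating is one treatment, or 1/8 = 12.5% of the expected mean of 8. One patient changing status at visit 8 moves that arm's rate by 1/12 = 8.3 percentage points, against a planned difference of 80 − 50 = 30.

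**6. The plan's power figure.** With 12 per arm and 50% against 80%, the pooled normal approximation gives (0.30 − 1.645 × 0.1947)/0.1848 = −0.11, or 45.6% power at one-sided 5%. That is close to the stated 45%. The calculation takes the two rates as given, so this point does not change it.

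**The case against.** The strongest reply is about consequence. One rule applied to both arms shifts both in the same direction. As an illustration on assumed inputs, take baseline mean 32 (SD 6, floor 21), exponential decline at 0.12 against 0.20 per visit with log-normal patient variation (log SD 0.4), and rating noise SD 2 to 4. Choosing Primary outcome over the Remitter criteria then moves each arm's visit-8 rate by about 2 to 9 points, but the between-arm difference by only about 1 to 4. Varying the log SD from 0.2 to 0.6 widens the latter to 0.4 to 7.3 points. None of these inputs comes from the documents. The reply stands as to size: the effect on the comparison should be modest. It does not supply the missing definition.

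A second reply is that the Remitter criteria are plainly the operative rule, since section 6 points to a criteria page for non-remitters and the Non-remitter criteria build on them. This is relevant but not decisive: Primary outcome and the Study Overview are both worded as the primary outcome, and section 13 cites none of the three.

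A reader might also infer more than the text supports:

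- *That most of the disagreement concerns patients who are still improving.* In each baseline group, 28 of the 31, 35 or 40 discordant pairs are falls of 4 points or more. But equally weighted pairs, including 10 to 0, say nothing about what most patients do.
- *That about a third of patients are affected.* Similar simulations give 29 to 37% with differing event visits when the strict cut-off is counted as a difference. With 10 or less throughout, the share is about 11 to 31%. Both ranges rest on assumed inputs.
- *That the ambiguity favours ketamine.* Nothing in the documents shows a direction.
- *That the single-score stopping wording in section 6 is a fourth rule.* It may be shorthand. It needs aligning, but the conclusion does not depend on it.

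**Conclusion.** The inconsistency is real and concerns the primary endpoint. The three rules differ in words and in whole criteria, not only in a symbol that extraction could have altered, and they conflict even when the cut-off is read alike. As written, the primary event is not uniquely defined, and the choice changes event time for some score series and status for others.

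The number of patients affected is unknown. I expect a modest effect on power, type I error and the between-arm comparison, and claim no bias towards either arm. What is damaged is the definition and reproducibility of the primary event, and therefore of the effect size the pilot is meant to hand on. This should be corrected before analysis, because the correction is cheap and cannot credibly be made once results are known.

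**What to change.** Before unblinding, adopt one rule as the primary event, dated at the second qualifying rating.

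- **Default:** the Primary outcome rule with a cut-off of 10 or less. Its section carries that heading, and it avoids extra ECT for patients with baseline 21 to 24 who settle at 9 or 10.
- **Alternative:** the Remitter criteria, on which the Non-remitter criteria rely, if the investigators accept those extra sessions. They could run to the ten-treatment minimum; for the baseline-22 patient above that is roughly 10 − 3 = 7 more.

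Use the chosen rule by cross-reference in Primary outcome, the Study Overview, the Remitter and Non-remitter criteria and section 13. Replace the single-score wording in section 6 with it, and state whether the HRSD-24 taken 24 to 72 hours after the last ECT can be the second rating.

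Report the other rule as a sensitivity analysis. If stopping follows the Remitter criteria, nesting means the Primary outcome event can be scored for every patient who stops as remitted. If stopping follows Primary outcome, some patients will stop before meeting the Remitter criteria. They stop because they are already doing well, so censoring them at that point would be informative. Report their number and bound the result: count them first as remitting at the next rating, then as not remitting.

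The cost is wording changes, one extra analysis, and one more rating or treatment for some patients compared with section 6 as worded. No new instrument is needed.

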### **Secondary Aim A**

To compare the cognitive side effects of ECT when used with ketamine to that with methohexitol

### **Secondary Aim B**

To use resting state and task related fMRI to identify ECT related functional network changes in the brain. Using resting state fMRI before and after ECT, we will (a) identify networks modulated by ECT (defined as a decrease or increase in functional connectivity from baseline to follow up scans), and we will (b) follow up their expression in the upcoming weeks, we will (c) identify functional networks of the brain which are correlated with superior clinical ECT outcome and we will (d) identify functional networks of the brain which are correlated with side effect profiles.

### **Secondary Outcome**

To determine the cognitive side effects we will use the following neuropsychological battery:

- Mini- Mental State Examination (MMSE),
- Postictal Recovery of Orientation,
- Rey Auditory Verbal Learning Test (RAVLT)

- Autobiographical Memory Interview – Short Form (AMI – SF),
- Subjective Memory Questionnaire (SMQ),
- Reading subtest of the Wide Range Achievement Test, 3rd Edition (WRAT-3)
- The Stroop Color Word Test (SCWT) (Golden version)
- Trail Making Test Part A & B
- Wechsler Adult Intelligence Test-Third Edition (WAIS-III), Digit Span Subtest
- WAIS-III Digit Symbol
- Controlled Oral Word Association Test (COWAT)
- N-Back

### **Exploratory Aims**

To compare other parameters of ECT when used with ketamine anesthesia to that with methohexitol anesthesia. These parameters are:

1. Seizure duration.
2. Seizure morphology.
3. Hemodynamic changes during ECT procedure.
4. Postictal behavioral complications such as agitation or psychosis.
5. To detect differences in brain activation.

### **Hypothesis**

We hypothesize that patients who receive ketamine anesthesia during ECT will need fewer treatments to achieve remission. At the end of the ECT course they will display fewer cognitive side effects compared to those treated with methohexitol anesthesia.

In the imaging part of this study, the main theoretical question is whether ECT exerts its effect primarily by altering networks. Our specific hypothesis is that ECT will decrease functional connectivity in the Default Mode Network.

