### **Significance**

Every year more than 100,000 patients in the United States and approximately 1,000,000 patients in the world receive ECT. According to the CORE group the average course of acute ECT for the treatment of a major depressive episode is 8 sessions. The major limiting factor in the use of ECT is the cognitive side effects, which are cumulative in nature. If the use of ketamine were able to reduce the overall number of treatments to remission or be even minimally cognitive sparing, this will have a significant positive impact in the field. Examples of the positive effects are reducing the burden of illness on patients and their exposure to possible side effects of ECT. Also, reducing patients' length of hospitalization, and decreasing the cost of mental health care. It is for these reasons that ketamine is being reexamined as a preferred anesthetic for ECT.

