### c. Timing of Assessments

**Table 2: Timing of Assessments**

Assessment	Baseline 	3X weekly before ECT	3X Weekly following ECT	ECT # 4	After last ECT 
Informed Consent	X				
Past Psychiatric History	X				
Medical Evaluation	X				
HRSD-24	X	X			X 
BPRS	X				X
BPRS positive items		X	X 		
SCID	X				
Neuropsychological Battery	X			X 	X 
Reorientation time			X		X
MMSE		X			
TESS	X				X

 Performed within 24 hours before the first ECT;  24hrs post ECT;  24-72 hrs post last ECT;

 1 week post last ECT  BPRS+ after full recovery, at 2h, at 4h if BPRS+2h >2

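### The cognitive hypothesis concerns the end of the ECT course, but the plan tests only slopes per visit on an undefined time scale and specifies no end-of-course comparison

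*Combined protocol and SAP*

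**What the plan says.** The Hypothesis section makes two linked predictions: "patients who receive ketamine anesthesia during ECT will need fewer treatments to achieve remission", and "At the end of the ECT course they will display fewer cognitive side effects". The Significance section describes "the cognitive side effects, which are cumulative in nature".

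Section 13 (Data Analysis, Aim 2) fits one mixed model per cognitive measure: "As above, the fixed effects are treatment group and time on study, and the random effect is subject". The quantity compared is the slope: "the model will provide estimates of the slopes measuring the rates of change in scores per visit for the two treatment groups". Time on study is not defined, and no contrast at a named assessment is specified. If a straight line does not fit, a transformation or another form, such as a quadratic, may be used.

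The power paragraph of section 13 applies one slope calculation to all aims other than remission. Its HRSD example converts a slope to a course-level effect, "corresponding to an average improvement of 2.0 more points per 8 visits".

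Under section 7b and Table 2 the neuropsychological battery is given three times: at baseline, around ECT #4 (24 hours after) and after the course. The footnote on the final battery cell reads "1 week post last ECT". The MMSE is also done before every session.

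**The concern.** Course length is not fixed by design. Treatment continues until remission or non-remitter status, and the protocol expects the ketamine arm to need fewer sessions. A slope per session or per week divides cognitive change by a quantity that treatment is expected to alter, so it answers a different question from the one in the Hypothesis section.

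Two distortions follow. If each treatment costs the same in both arms, the arm with fewer treatments ends better off, yet the slopes are equal. If both arms end with the same loss, the arm with the shorter course has the steeper slope and looks worse.

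Section 13 gives the pilot's goal as estimating effect sizes for a later trial, so a mis-targeted estimate would carry forward into that design.

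**Working it through.** **The plan's own figures.** Detectable slope difference 0.05σ per visit; with σ = 5.0, 0.05 × 5.0 = 0.25 points per visit, and 0.25 × 8 = 2.0 points. This reproduces. The conversion uses 8 visits in both arms, which assumes the equal course length that the hypothesis denies.

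The 80% power cannot be confirmed or refuted, because it needs a within-subject correlation ρ that is not stated. From m = 2(z₁+z₂)²(1−ρ)/(Sxx·d²), with m = 12, d = 0.05 (in units of σ) and (1.96+0.84)² = 7.85:
- battery at sessions 0, 4, 8 (Sxx = 32): 1−ρ = 12 × 32 × 0.0025/15.7 = 0.061, so ρ ≈ 0.94;
- visits 1 to 8 (Sxx = 42): ρ ≈ 0.92.

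**Inputs for the check.** From the documents: 12 per arm, two-sided 5%, three battery occasions, about 8 treatments expected, three sessions per week. Assumed, because the documents give no cognitive SD, expected loss or arm-specific course length: 6 treatments on ketamine and 8 on methohexital, and a loss of 0.10 SD per treatment or 0.8 SD in total.

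**Case A, equal loss per treatment.** End loss is 6 × 0.10 = 0.6 SD against 8 × 0.10 = 0.8 SD. The ketamine benefit is 0.2 SD, or 0.2/0.8 = 25%. The per-session slope difference is 0.10 − 0.10 = 0. For ketamine courses of 5 to 7, the benefit the slope does not show is 0.3 to 0.1 SD.

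**Case B, equal end loss of 0.8 SD.** Slopes are −0.8/6 = −0.133 and −0.8/8 = −0.100 SD per session. The ratio is 8/6 = 1.33 and the difference −0.033 against ketamine. For ketamine courses of 5 to 7 the difference is −0.060 to −0.014, against the planned detectable size of 0.05.

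**Calendar time.** From first treatment to the one-week battery is 5/3 + 1 = 2.67 weeks against 7/3 + 1 = 3.33 weeks. In case B the ketamine change per week is 3.33/2.67 = 1.25 times as large. In case A it is 0.6/2.67 = 0.225 against 0.8/3.33 = 0.240, so a 25% benefit shrinks to about 6%.

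**Assessment index.** With occasions coded 0, 1, 2, the least-squares slope is (last − first)/2, half the baseline-to-end change. Both distortions then largely vanish.

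**Rejection rates.** Simulation used 12 per arm, ρ = 0.6, courses of 5–7 against 7–9, a random-subject slope test in sessions, and a loss of 0.8 to 1.0 SD:

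| Case | Session slope | Baseline-adjusted end comparison |
|---|---|---|
| A, equal loss per treatment | about 5% | about 8–10% |
| B, equal end loss | about 9–12% | about 5% |

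A normal approximation for the end comparison in case A gives a standard error of √(1−0.36) × √(2/12) = 0.8 × 0.408 = 0.327 SD. Differences of 0.20 and 0.25 SD then give power of about 9% and 12%, close to the simulated range.

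With ρ = 0.7 and an end loss of 0.8 SD, case B shows significant ketamine harm in 12% of runs with the battery, 15.5% with per-session testing, and 23% with the battery for courses of 6 against 10. The nominal one-directional rate is 2.5%.

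**The case against.** **The time coding is not fixed.** The uses of visit that clearly mean a session come from the remission and HRSD examples, and the HRSD is rated before every session. For a battery given three times, per visit can equally mean per assessment, and on that reading the problem largely disappears. This stands for the battery. It does not carry over to the per-session MMSE, and the text still does not say which coding applies.

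**The slope is a legitimate quantity.** Secondary Aim A names no time point, the Study Overview plans cognitive monitoring around each treatment as well as at the end, and the Significance section lists fewer treatments and cognitive sparing as alternative benefits. A zero slope difference in case A correctly says that ketamine spares nothing per treatment. This also stands, and is a reason to keep the slope as support. It does not make the slope a test of a hypothesis set at the end of the course.

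**Non-linear forms are allowed.** A transformation or quadratic changes the shape of the curve but does not supply an end-of-course contrast.

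**Stronger readings.** A reader might infer that the plan would often declare ketamine harmful. The documents do not support that. Simulated rates for the two tests reach 26 to 46% only at losses of 2.0 to 2.5 SD, and nothing in the protocol suggests losses of that size. A reader might also infer that section 13 definitely counts battery time in sessions; it leaves this open.

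**Conclusion.** The concern holds in a limited form. The stated hypothesis is about the end of the course. The stated test is a slope difference on an undefined time scale, and no end-of-course contrast is written although the data for one are collected.

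Under session or calendar time, the slope can hide a benefit from shorter courses or turn equal end results into an apparent disadvantage. That direction follows from arithmetic once course lengths differ. The 25% and 1.33 figures rest on assumed courses of 6 and 8, and the rejection rates also rest on assumed loss and correlation. With 12 per arm, a significant false harm result is possible but unlikely. The chief consequence is an effect estimate aimed at the wrong quantity, in a pilot whose purpose is estimation.

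**What to change.** In section 13, Aim 2:

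1. Make the test of the cognitive hypothesis the baseline-adjusted between-arm difference, with 95% CI, at the battery one week after the last ECT, whatever the number of treatments. Use ANCOVA, or a mixed model with assessment as a category and baseline as covariate.
2. Report the contrast 24 hours after ECT #4 separately, as the acute effect.
3. Define time on study for each measure: session, calendar time or assessment number.
4. Keep the per-session slope as a supportive measure of sparing per treatment.

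This costs only analysis-plan wording and needs no new data. The downside is that the slope is no longer the headline test.

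Power stays low. With 12 per arm, the end difference detectable with 80% power is 2.80 × √(2/12) × √(1−ρ²), which is 0.99, 0.82 and 0.50 SD at baseline-to-end correlations of 0.5, 0.7 and 0.9. The 95% CI half-widths are 0.69, 0.57 and 0.35 SD. The change corrects what is estimated; it does not make the pilot confirmatory.
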